**Background and Objective(s):**

Keratoplasty, also known as corneal transplantation, is a surgical procedure in which a damaged or diseased cornea is replaced entirely (penetrating keratoplasty) or partially (lamellar keratoplasty) by a donated corneal graft. Post-keratoplasty astigmatism is multifactorial in its etiology, in which the preoperative factors involve the age and health of donor tissue, recipient pathology, the intraoperative factors include trephine quality, graft size, wound apposition and suturing technique and suture material and the postoperative factors cover wound healing, postoperative drugs, inflammation, corneal vascularization, rejection.

The contrast sensitivity function (CSF) provides a comprehensive measure of the visual system which has been used to characterize spatial vision deficits in many visual disorders such as amblyopia, multiple sclerosis, glaucoma, retinitis pigmentosa, as well as autism spectrum disorder. Although some studies have reported the contrast sensitivity function of keratoplasty patients, few has documented the CSF in different spatial frequencies as well as its relationship between the life quality. To our knowledge, the current study would be the first case series to inquiry the contrast sensitivity function in the keratoplasty patients with quick CSF, as well the relationship between visual quality and life quality.

**Design:**

All participants would undergo an ophthalmic examination that included slit-lamp biomicroscopy , visual acuity, corneal topography, contrast sensitivity measurements, 9-SF life quality questionnaire and fundus examination. Then the normal group would be covered by positive spherical lens of 1.0D to 6.0D to repress the BCVA to 0.1 to 0.9 respectively to compare the visual functions with the keratoplasty patients on the same visual acuity.

**Methods:***Subjects and Inclusion Criteria*

This observational, cross-sectional, non-consecutive case study would be conducted with patients who have accepted keratoplasty and healthy subjects who visited the Corneal Clinic of Zhongshan Ophthalmic Center, Guangzhou, China. The research was performed according to the tenets of the Declaration of Helsinki. The study protocol was approved by the Zhongshan Ophthalmic Ethical Committee. All subjects provided informed consent after receiving both written and verbal explanations of the nature and intent of the study.

The Inclusion Criteria for keratoplasty patients are: 1) Accept the corneal transplantation based on the clinical diagnosis of ocular surface disease; 2) more than 7 and less than 60 years old; 3) absence of other ocular disorders and no history of eye surgery and other systemic diseases. And the exclusion Criteria are: 1) less than 7 or more than 60 years old; 2) with the history of eye surgery and other systemic diseases.

All participants underwent an ophthalmic examination that included slit-lamp biomicroscopy , visual acuity, corneal topography, contrast sensitivity measurements, 9-SF life quality questionnaire and fundus examination. Then the normal group would be covered by positive spherical lens of 1.0D to 6.0D to repress the BCVA to 0.1 to 0.9 respectively to compare the visual functions with the keratoplasty patients on the same visual acuity.

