#### *CSF Measurements*

The quick CSF method, implemented in a 10 alternative forced-choice digit identification task, was used to assess the contrast sensitivity function. Stimuli were displayed on a gamma-corrected 46 inch LCD monitor (Model: NEC LCD P463) with a 1920×1080 pixel resolution, 50 cd/m^2 mean luminance and 60 Hz vertical refresh rate. Observers viewed the display monocularly from a distance of 4 m in a dark room. For each trial, they were asked to verbally report the identities of three digits presented on the screen to the experimenter, who used the computer keyboard to enter their responses. The stimuli disappeared after all the responses were entered. Observers were given the option to report “I don’t know” upon which the response

was coded as incorrect. No feedback was provided. All three responses were used to update the posterior distribution of the CSF parameters, which in turn was used to adaptively choose the most informative combination of spatial frequency and contrast for the next trial. A new trial started 500 ms after the responses. There were 30 trials in approximately 5 min. The quick CSF data were scored to generate the cutoff spatial frequency, defined as the spatial frequency corresponding to a perceptual sensitivity of 1, and the area under the log CSF (AULCSF), a summary measure of the window to spatial vision.

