### **Statistical Analysis Plan:**

Data would present as means  $\pm$  standard deviations. Between group t-test would be used for statistical comparisons of the CSF results, including cutoff SF and AULCSF between the astigmatism group and the control group. A multiple linear regression analysis would be performed to investigate the relation between the AULCSF and the lens power of astigmatism. Statistical analyses were performed using SPSS version 17.0 (SPSS, Inc., Chicago, IL, USA), and p values of  $< 0.05$  would be considered statistically significant.

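### Controls' unblurred contrast test is fixed before their lens tests, and only controls are retested, so practice or fatigue may bias the acuity-matched comparison in either direction

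*Combined protocol and SAP*

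**What the plan says.** The Design section, repeated almost word for word under Subjects and Inclusion Criteria, has two steps.

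- **Step one, both groups:** "All participants would undergo an ophthalmic examination that included slit-lamp biomicroscopy , visual acuity, corneal topography, contrast sensitivity measurements".
- **Step two, controls only:** "Then the normal group would be covered by positive spherical lens of 1.0D to 6.0D", in order "to repress the BCVA to 0.1 to 0.9 respectively". The aim is "to compare the visual functions with the keratoplasty patients on the same visual acuity".

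Under CSF Measurements, the length of a run is given as "There were 30 trials in approximately 5 min", and "No feedback was provided".

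The Statistical Analysis Plan has two analyses: "Between group t-test would be used for statistical comparisons of the CSF results, including cutoff SF and AULCSF", and a multiple linear regression "to investigate the relation between the AULCSF and the lens power of astigmatism". It does not say whether the control value in the t-test is the unblurred or a blurred one. Neither analysis has a term for test order.

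The documents do not state the order of the lenses, the step between them, how many each control wears, whether runs share a session, or how many runs a patient does. No repeat is described for patients.

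**The concern.** The task is effortful: three digits per trial, 30 trials, in a dark room. Scores may rise with familiarity or fall with tiredness. The lens step exists to give controls a reading at the patients' acuity. As written, that reading is always a second or later run, while the patient's reading appears to be a first. Any change with repetition is then added to the group difference.

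The sign matters. Practice would lift the blurred control scores and create or enlarge an apparent patient deficit. Fatigue would lower them and mask a real one. The documents give no basis for choosing between the two, and if run number is not recorded the effect cannot be estimated afterwards.

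Within controls, the contrast of unblurred with blurred vision is tied to order in the same way, because the unblurred run always comes first.

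**Working it through.** The plan states no sample size, SD or effect size, so there is no figure of its own to reproduce. The steps below show what the text fixes and what has to be assumed.

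**1. Number of runs.** From the documents: 30 trials and about 5 minutes per run. The number of lenses per control is an assumption.

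| Lenses per control (assumed) | Runs, with unblurred | Trials | Minutes |
|---|---|---|---|
| 1 | 2 | 60 | 10 |
| 6 (whole dioptres) | 7 | 210 | 35 |
| 9 (acuity in steps of 0.1) | 10 | 300 | 50 |

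A patient tested once does 30 trials in about 5 minutes.

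**2. Prior runs behind a blurred reading.** With one lens, 1. With seven runs, the blurred ones have 1 to 6 prior runs, mean (1+6)/2 = 3.5. With ten runs, 1 to 9, mean (1+9)/2 = 5.

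**3. False-positive rate.** Assumptions: linear drift per run in either direction, SD 0.20, 30 per group, two-sided 0.05, no true group difference, and one blurred control reading at the stated mean position against a patient's first run.

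- Bias = drift × prior runs.
- Noncentrality = bias / (0.20 × √(2/30)) = bias / 0.0516.
- Rate = probability that a noncentral t on 58 degrees of freedom falls outside ±2.002.

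Example: drift 0.01 and 3.5 prior runs give a bias of 0.035, noncentrality 0.035/0.0516 = 0.68, and a rate of 10.2%.

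| Drift per run | 1 prior run | 3.5 prior runs | 5 prior runs |
|---|---|---|---|
| 0.005 | 5.1% | 6.3% | 7.6% |
| 0.01 | 5.4% | 10.2% | 15.9% |
| 0.02 | 6.7% | 26.6% | 47.8% |

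The rate also depends on sample size. By the normal approximation, a shift of 0.2 SD gives 9.7% with 20 per group, 12.1% with 30, 17.0% with 50 and 29.3% with 100.

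**4. Order against lens power.** Take six whole-dioptre lenses plus the unblurred run, at positions 0 to 6 and powers 0 to 6 D.

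- Rising order throughout: correlation of position with power 1.00, so drift and blur cannot be separated.
- Unblurred first, lenses random: each lens has mean position 3.5. The expected sum of cross-products is (0−3)(0−3) + 0.5 × (21−18) = 10.5, the sum of squares is 28, and the mean correlation is 10.5/28 = 0.375.
- All seven conditions random: mean correlation 0.

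Randomising the lenses alone therefore leaves part of the problem. The unblurred run has to be in the scheme.

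**The case against.** The strongest reply is that much of the possible harm depends on things the protocol does not say.

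- **Rising lens order.** A reader might infer it from the way the lenses are listed, and conclude that blur and run number are perfectly confounded. The text gives a range, not a sequence. If acuity is on the decimal scale (the scale is not stated), stronger plus lenses lower it, so the listed acuities run opposite to the listed powers and list order cannot be test order. Only unblurred before blurred is fixed.
- **A full series per control.** Seven to ten runs is likewise an inference. One lens per control, chosen to match a patient's acuity, would suit the stated purpose. At a drift of 0.01 that gives 5.4%. The rates at the last run of a full series, 20.8% (6 prior runs) and 40.3% (9 prior runs), need every assumption at once.
- **Patients tested once.** This is inferred from the absence of any described repeat.
- **Which analysis is affected.** A t-test on the unblurred control run would compare first run with first run and avoid this bias. The regression may concern patients' astigmatism, since the control lenses are spherical, so a biased control slope cannot be asserted.
- **Feedback.** Giving none may limit learning, though it excludes neither practice nor fatigue.

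All of this stands as a limit on size and wording. It does not remove the fixed order of unblurred before blurred, or the fact that lens testing is for controls only. A t-test on unblurred controls would escape the bias only by not making the acuity-matched comparison that the Design section promises.

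**Conclusion.** The point holds in a limited form. The text ties blurred versus unblurred testing to order within controls, and sets a control's second or later run against what appears to be a patient's first in the acuity-matched comparison. Nothing in the plan controls for this. Bias is possible in either direction, but its size is unknown. With SD 0.20, 30 per group and a drift of 0.01 AULCSF per run, all assumed, the false-positive rate runs from 5.4% (one lens per control) to 10% to 16% at the average blurred run (7 to 10 runs per control). Confounding with lens power among the blurred runs arises only if the lenses are given in a fixed order, which the documents do not state. The change is worth making because it costs little before testing starts and cannot be made good afterwards.

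**What to change.** Add to the Design section: for each control, the order of all CSF conditions, including the unblurred one, is randomised or counterbalanced; every patient and control first does the same short practice run; breaks are allowed; run number is recorded. State also the lens steps and how many lenses each control wears.

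In the Statistical Analysis Plan, say which control readings enter the t-test. Make the comparison at matched acuity with all control runs in a mixed model, with a random subject effect and run number as a covariate. Do not restrict it to controls' first runs: with 30 controls (assumed) spread over 7 to 10 conditions, only 30/10 = 3 to 30/7 ≈ 4 would have any one condition first, and most control data would be discarded.

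Cost: at most about 5 minutes of practice per person, a randomisation list and one extra recorded variable.

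### The lens rule for the blurred controls does not secure the same-acuity comparison, and the planned t-test does not repair it

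*Combined protocol and SAP*

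**What the plan says.** The Design section has every participant examined first; the list includes "slit-lamp biomicroscopy , visual acuity, corneal topography, contrast sensitivity measurements". The normal group is then blurred with a "positive spherical lens of 1.0D to 6.0D to repress the BCVA to 0.1 to 0.9 respectively". The stated purpose is "to compare the visual functions with the keratoplasty patients on the same visual acuity". The Methods subsection on subjects and inclusion criteria repeats this rule in the same words.

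The CSF Measurements subsection describes monocular testing on the quick CSF and does not mention the lenses.

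The Statistical Analysis Plan states: "Between group t-test would be used for statistical comparisons of the CSF results, including cutoff SF and AULCSF". The groups there are called astigmatism and control. It adds a multiple linear regression "to investigate the relation between the AULCSF and the lens power of astigmatism". Neither analysis mentions acuity level, matching, or the acuity reached through a lens.

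**The concern.** The blurred controls exist to separate two things: loss of contrast sensitivity that goes with reduced acuity, and loss beyond that in grafted eyes. The comparison separates them only if patient and control really have the same acuity when contrast sensitivity is measured.

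The plan relies on a lens rule for this, and the rule is doubtful in three ways. Its order makes sense on one acuity scale and not on the other, and the scale is not named. It does not say which lens goes with which level. It does not ask for acuity to be checked once the lens is in place. If the match fails, the analysis has no second line of defence, and a difference in acuity could be read as an effect of the graft.

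**Working it through.** The documents give no sample size, power or effect size, so there is no planned figure to reproduce. The check concerns the order of the rule, what it leaves open, and what the t-test then estimates.

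**Inputs from the documents**
- Lens range: 1.0 D to 6.0 D (Design; Methods).
- Acuity range: 0.1 to 0.9, linked to the lens range by the word *respectively* (same places).
- Acuity scale, lens step, acuity step, pairing, number of levels per control: not stated.
- Group comparison: t-test on cutoff spatial frequency and AULCSF (Statistical Analysis Plan).

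**Assumptions from general optics, not from the documents**
- In a given normal eye, more plus power means more blur.
- The same lens need not give the same acuity in two eyes, because residual refraction and pupil differ.

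**Step 1: order of the pairing.** Read in order, 1.0 D goes with 0.1 and 6.0 D with 0.9. The scales are linked by logMAR = −log10(decimal acuity) and decimal acuity = 10^(−logMAR).

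| Lens | Label | If the label is decimal | If the label is logMAR |
|---|---|---|---|
| 1.0 D | 0.1 | −log10(0.1) = 1.00 logMAR, the worst level | 10^(−0.1) = 0.79 decimal, the best level |
| 6.0 D | 0.9 | −log10(0.9) = 0.05 logMAR, the best level | 10^(−0.9) = 0.13 decimal, the worst level |

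On the decimal scale the weakest lens would give the worst acuity, so the order is reversed. On the logMAR scale the order is right. The two readings assign opposite ends of the lens range to the same end of the acuity range, so the missing scale matters.

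**Step 2: is the acuity reached ever measured?** Acuity belongs to the examination that comes before the lenses. No later text asks for it to be repeated through the lens. Under the second assumption, lens power alone does not fix acuity, so a match is not guaranteed on either scale.

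**Step 3: what the t-test estimates.** Suppose, for illustration, that mean AULCSF depends on group and acuity as α + γ·(patient) + β·(acuity), where γ is the difference at equal acuity. The difference in raw means is then

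γ + β × (mean acuity of patients − mean acuity of controls as tested).

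It equals γ only if β is zero or the two mean acuities are equal. The first would remove the reason for blurring the controls. The second is what the lens rule was meant to deliver and, by steps 1 and 2, does not ensure. The same holds for cutoff spatial frequency. A curved relation with acuity would change the formula but not the conclusion; equal means would then not even be sufficient.

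**Step 4: other analysis text.** The regression uses the lens power of astigmatism, a term not tied to the spherical control lenses, and does not name measured acuity. The plan also does not say which control readings enter the t-test, with or without lenses, or whether one control contributes several. If several from one person enter, an independent-groups t-test would treat correlated readings as independent.

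**The case against.** The strongest reply is that the sentence makes acuity the target and the lens the means. On that reading *respectively* is loose English for a range of lenses used to reach a range of acuities, and the examiner would naturally change the lens until the target is met. Nothing says that controls are labelled by nominal lens power. If acuity is in logMAR, the order is right as well.

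Much of this stands. The documents do not prove that the rule is reversed. Speaking of acuity being pushed down to such values fits a decimal scale better, since logMAR rises as acuity worsens, but that is an inference. The missing check through the lens is an omission, not an instruction against checking.

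The reply does not reach the main point. Under the generous reading, the plan still does not require the acuity obtained to be measured and recorded, and the analysis still does not use it.

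A reader might go further in three ways that the documents do not support:
- **That the rule is impossible to follow because six lenses must serve nine levels.** This needs a 1 D lens step and a 0.1 acuity step, and neither is stated. At 0.5 D there are (6.0 − 1.0)/0.5 + 1 = 11 lenses, and at 0.25 D there are 21, enough to cover nine levels.
- **That matching is wrong by 1.00 − 0.05 = 0.95 logMAR at each end.** This is the distance between two labels on an assumed decimal scale. It would be an error only if someone recorded the label without looking at the acuity obtained.
- **That the bias in AULCSF can be put in figures.** This needs a slope of AULCSF on acuity, and the documents give none.

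**Conclusion.** The concern holds in this form: the plan as written does not secure the same-acuity comparison for which the blurred controls are included. The order of the rule is reversed if acuity is decimal and correct if it is logMAR; the scale, steps and pairing are unstated; no acuity reading through the lens is required; and the planned t-test neither matches nor adjusts.

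The size of the resulting bias cannot be given. It is the product of the leftover acuity difference and the dependence of CSF on acuity, and neither is in the documents. The conclusion rests on two modest assumptions: that CSF outcomes vary with acuity, which the design itself presupposes, and that one lens can give different acuities in different eyes. It does not depend on which acuity scale was meant. The plan should be changed, because this goes beyond missing detail: no other part of it protects the comparison.

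**What to change.** **Protocol (Design and Methods).** Name the acuity scale and delete *respectively*. List the target levels and say how many each control contributes. Then state: for each target level, plus power is adjusted in the tested eye until measured acuity reaches the target; the lens power and the acuity reached are both recorded; CSF is measured through that lens.

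**Statistical Analysis Plan.** For the same-acuity comparison, replace the unadjusted t-test with a comparison of cutoff spatial frequency and AULCSF that is matched on measured acuity, or with a regression on group and measured acuity. If a control contributes several levels, allow for the repeated readings, for example with a random intercept for participant. Say which control readings, with or without lenses, enter each analysis.

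**Cost.** Some rewording and additional acuity checks for each control. The number depends on the lens step and the number of target levels, which are for the sponsor to choose. As an upper bound for one example, stepping through the whole range in 0.25 D steps means (6.0 − 1.0)/0.25 + 1 = 21 settings, so the burden should be considered when the step is set. If the lens is already adjusted to a measured acuity, the protocol change is only to write that down and keep the readings.

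### Patients whose acuity is worse than the blurred-control range have no same-acuity control, and no rule keeps them out of the group t-test

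*Combined protocol and SAP*

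**What the plan says.** The Design section, repeated under Methods (Subjects and Inclusion Criteria), has every participant undergo visual acuity and contrast sensitivity testing. After that, "the normal group would be covered by positive spherical lens of 1.0D to 6.0D". The stated purpose is "to repress the BCVA to 0.1 to 0.9 respectively to compare the visual functions with the keratoplasty patients on the same visual acuity". The scale of the acuity values, decimal or logMAR, is not given.

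The patient inclusion criteria cover the indication ("Accept the corneal transplantation based on the clinical diagnosis of ocular surface disease"), age ("more than 7 and less than 60 years old") and history ("absence of other ocular disorders and no history of eye surgery and other systemic diseases"). The exclusion criteria cover age and history only: "less than 7 or more than 60 years old; 2) with the history of eye surgery and other systemic diseases". None of them mentions acuity.

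The Statistical Analysis Plan states: "Between group t-test would be used for statistical comparisons of the CSF results, including cutoff SF and AULCSF", and makes the comparison "between the astigmatism group and the control group". It does not define either group further, and does not say whether the controls are taken blurred or unblurred. It gives no analysis set, acuity matching, strata or acuity covariate. The one regression relates AULCSF to the lens power of astigmatism.

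**The concern.** The blurred arm is there to separate two explanations for poor contrast sensitivity after a graft: worse acuity, or a loss beyond what acuity explains. That separation works only where patients and controls overlap in acuity. Eligibility is open at the poor end, the blurred range is not, and the SAP does not say what happens to patients beyond it.

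The Background lists inflammation, vascularization and rejection among postoperative factors, so some grafted eyes with very poor acuity are plausible. If they are averaged into the patient group, they pull down its mean AULCSF and cutoff frequency with nothing comparable on the control side. The difference could then be reported as a graft-specific deficit at equal acuity when part or all of it is acuity.

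**Working it through.** **Text check**

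| Element | Source | Acuity rule |
|---|---|---|
| Patient inclusion and exclusion | Methods, Subjects and Inclusion Criteria | none |
| Blurred controls | Design; repeated in Methods | BCVA 0.1 to 0.9, notation not stated |
| Unblurred control run | Design (all participants tested, then blur) | control's own acuity |
| Group t-test | Statistical Analysis Plan | none |

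The control runs therefore extend from unblurred acuity down to the poor end of the blurred range. Beyond that end there are eligible patients and no control data.

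**Size**

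The documents give no sample size, SD or acuity distribution, so there is no planned figure to reproduce. What follows is illustration only.

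Assumed inputs:
- Decimal notation.
- Share *f* of patients below 0.1: 10% to 30%.
- Average excess beyond 0.1, *e*: 0.3 to 0.6 logMAR.
- Slope *b*: 0.7 to 1.3 AULCSF per logMAR.
- SD 0.30 and 30 per group; two-sided 5% test.
- No true deficit at equal acuity, in-range acuity balanced between the groups, and one independent value per person.

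Bias in the mean difference = *f* × *e* × *b*:
- low: 0.10 × 0.3 × 0.7 = 0.021
- middle: 0.20 × 0.3 × 1.0 = 0.060
- high: 0.30 × 0.6 × 1.3 = 0.234

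The rejection rate was calculated in three ways:
- **A.** Noncentral t with SD 0.30 in both groups, 58 df, noncentrality = bias / 0.30 × √(30/2). This gives 0.27, 0.77 and 3.02.
- **B.** Normal approximation with the patient variance widened by the mixture to 0.30² + *f*(1−*f*)(*eb*)². Standardised shift = bias / √[(patient variance + 0.30²)/30]. This gives 0.27, 0.75 and 2.31.
- **C.** As A, but with the SD including the acuity spread inside the range. The nine decimal steps 0.1 to 0.9 have a logMAR SD of about 0.29, so total SD = √(0.30² + (0.29*b*)²), about 0.36, 0.42 and 0.49.

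| Case | Bias (AULCSF) | A | B | C |
|---|---|---|---|---|
| Low | 0.021 | 5.8% | 5.8% | 5.6% |
| Middle | 0.060 | 11.9% | 11.6% | 8.4% |
| High | 0.234 | 84% | 64% | 45% |

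A separate calculation in SD units uses 30 per group, a share *f* of patients lower by *s* SD, and shift *fs* / √[(2 + *f*(1−*f*)*s*²)/30]. For *f* = 10% it gives 7% (*s* = 1) to 11% (*s* = 2). For *f* = 30% it gives 20% to 50%. With *f* = 0 the rate is 5%.

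The result is driven by the share of patients beyond the range and how far beyond it they lie. The documents give neither.

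**The case against.** Several points on the other side have force.

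- **Inclusion is inferred.** A reader might take it as written that all patients are tested against blurred controls. The SAP does not say so: it names an astigmatism group and a control group and leaves both undefined. If the controls are unblurred, the t-test is not a same-acuity test and the blur range does not bear on it. What stands is that no rule removes poor-acuity patients, and that an unrestricted group comparison ordinarily includes them. If the controls are unblurred, no patient gets the comparison that the design promises.
- **The good-acuity end.** A reader might infer a gap at both ends of 0.1 to 0.9. The documents do not support that. Contrast sensitivity is measured in all participants before the lenses are applied, so an unblurred control run exists. The uncovered end is the poor one. Patients with acuity better than the blurred range, if averaged against blurred controls, would shift the mean the other way.
- **Notation.** Reading the range as decimal is plausible but is not stated. Under logMAR the uncovered patients are those above 0.9.
- **Magnitude.** Every input is assumed. The 12% in the middle case is not a property of this trial: it falls to about 8% once in-range acuity spread is counted, and the low case is close to nominal. The calculation also carries a linear acuity slope below 0.1, where there are no control data.
- **A wider weakness.** The t-test does not match on acuity for anyone, inside or outside the range, so cutting the sample to the covered range would not by itself restore a 5% error rate. This is correct, and the fix must include an acuity-level comparison. Adding acuity as a covariate would not remove the need for the restriction, because beyond the range the model would extrapolate the control relation.

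**Conclusion.** The point holds as a coverage gap at the poor-acuity end. Eligibility is open, the blurred controls stop at a fixed acuity, and the SAP has neither a restriction nor a matched analysis. Followed on its ordinary reading, the plan can mix acuity loss with graft-specific contrast loss.

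The size cannot be determined from the documents. Under the stated assumptions the false-positive rate runs from about 6% to several times the nominal 5%. If no patient has worse acuity than the controls cover, this particular bias is zero. The documents do not establish that such patients certainly enter a test against blurred controls, that the notation is decimal, or that any one error rate applies. The change is worth making because it is cheap and protects the stated purpose of the blurred arm.

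**What to change.** Amend the Statistical Analysis Plan, with a matching line in Design:

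1. State the acuity notation, and define the two groups, including which control runs (blurred, unblurred or both) enter each comparison.
2. Carry out the same-acuity comparison of AULCSF and cutoff frequency by acuity level, matched or stratified, with an analysis that allows for repeated runs on the same control.
3. Restrict that comparison to patients whose acuity lies within the range the control runs actually cover, counting the unblurred run as the good-acuity end.
4. Report the number of patients with worse acuity and describe their contrast sensitivity separately, outside the same-acuity test.
5. Limit the same-acuity conclusion to the covered range.

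The cost is SAP wording and a somewhat more involved analysis; no new measurements are needed. The downside is that some patients leave the matched comparison, which reduces its size. They stay in the descriptive and quality-of-life results.
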